**Table 3: Summary of Immunogenicity Assays (Cellular)**

Assay	Purpose
Secondary endpoints	
Flow cytometry (ICS)*	Analysis of T-cell responses to RSV F-protein peptides for Th1/Th2 subtyping
Exploratory endpoints	
IFN $\gamma$ ELISpot	T-cell IFN $\gamma$ responses to RSV F-protein peptides
ICS	Analysis of T-cell responses to RSV F-protein peptide-stimulated PBMCs (including but not limited to, CD4/CD8, IL2, INF $\gamma$ , TNF $\alpha$ , activation markers and memory)
Cytokine analysis	Analysis of secreted cytokines in RSV F peptide-stimulated PBMC supernatant, including, but not limited to, measurement of Th1/Th2 cytokine balance

ELISpot = enzyme-linked immunospot; F = fusion; ICS = intracellular cytokine staining; IFN $\gamma$  = interferon gamma; IL = interleukin; PBMC = peripheral blood mononuclear cell; Th = T-helper (cell); RSV = respiratory syncytial virus; TNF $\alpha$  = tumor necrosis factor alpha

\* Cytokine analysis for Th1/Th2 profiling will be done in cases where no ICS data can be generated due to insufficient number of PBMCs for ICS assay

In addition to RT-PCR performed on a nasal turbinate sample collected at the time of infection, any immunogenicity blood sample collected from any Cohort 1 subject who subsequently develops a suspected RTI may also be assayed by a serological assay (eg, ELISA specific to RSV protein G and/or N) to confirm RSV infection.

For adults, nasal turbinate samples, collected pre-dose on Days 1 and 29, 7 days post-Dose 1 (Day 8) and 28 days post-Dose 2 (Day 57) will be used to assess any immunoglobulin (Ig) or cellular immune component.

### OTHER EVALUATIONS – RSV INFECTION

RSV seropositivity of Cohort 1 subjects will be assessed by RSV enzyme immunoassay (EIA) or virus neutralization assay at screening. The cut-off for seropositivity by EIA is a titer >10 EIA units and the cut-off by virus neutralization assay is a titer >4. *Note:* RSV-seropositive toddlers may be recruited if RSV seropositivity was assessed via either of these assays in a different study of the sponsor.

Nasal turbinate samples, taken from any Cohort 1 subject with an RTI during each 28-day post-vaccination period, and from any Cohort 1 subject with a specified combinationa of respiratory symptoms during the RSV season (but outside of the 28-day post-vaccination period), and from any Cohort 1 subject with a MA-RTI or severe LRTI during the whole study period, will be assessed for the presence of RSV infection by RT-PCR.

In addition, scheduled blood samples may be assessed for the presence of RSV antibodies by serology.

### SAFETY EVALUATIONS

On a daily basis, for 7 days after each vaccination, each adult subject and each pediatric subject's parent/legal guardian will be asked to record the following AEs via the diary card:

- Solicited local AEs *for all subjects*: erythema (measured using the ruler supplied), swelling/induration (measured using the ruler supplied and graded using the functional scale), and pain/tenderness.

a Persistent (>48 hours) clinical symptoms of rhinitis (sneezing or runny nose or congestion) and persistence (>24 hours) of one or more of the following: cough, abnormal breathing, fever, lethargy or decreased appetite.

- Solicited systemic AEs *for adult subjects*: fatigue, headache, myalgia, arthralgia, chills, nausea and fever (ie, body temperature  $\geq 38$  °C); *for pediatric subjects*: loss of appetite, vomiting, diarrhea, decreased activity/lethargy, irritability/crying and fever (ie, body temperature  $\geq 38$  °C).

Body temperaturea should be measured by the same method and at approximately the same time each day, preferably in the evening and, for pediatric subjects, additionally whenever the child feels warm using the thermometer supplied. All diary assessments, including body temperature 7 days after the first and second vaccinations may be collected earlier to coincide with the Day 8 clinic visit.

The investigator will review each subject's diary at the subsequent in-clinic visit; diary information will be transcribed by the study personnel into the electronic case report form (eCRF).

The investigator or study-site staff will document any reported unsolicited AEs and perform causality evaluations from the time of ICF signature through 28 days after the final vaccination. For both cohorts, all SAEs will be collected from ICF signature to the end of the study.

When nasal turbinate samples are collected from subjects with an RTI during each 28-day post-vaccination period, and from subjects with a specified combination of respiratory symptoms during the RSV season, but outside the 28-day post-vaccination period, the attending health care professional will record signs and symptoms of the RTI using the RTI Symptoms Form. RTIs, preferably as a diagnosis, will also be reported on the AE page of the eCRF if they occur within 28 days following vaccination. Any RTI fulfilling the criteria of an SAE would be reported as such during the entire study. Any severe LRTI will be reported using the SAE reporting system and SAE form, regardless of whether the event fulfills the criteria of an SAE.

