#### ***Injection Site (Local) Adverse Events***

Each subject will be asked to note in the diary occurrences of pain/tenderness, erythema and induration/swelling at the study vaccine injection site daily for 7 days post-vaccination. The extent (largest diameter) of any erythema, and induration/swelling should be measured (using the ruler supplied) and recorded daily. Induration/swelling should also be graded using the functional scale.

- **Injection Site Pain/Tenderness**

Injection site pain (eg, stinging, burning) is an unpleasant sensory and emotional experience associated with actual or potential tissue damage and occurring at the immunization site (with or without involvement of surrounding tissue). Injection site tenderness is a painful sensation localized at the injection site upon palpation and/or movement of the limb. Due to subjective nature of the reaction, the severity assessment of pain/tenderness is self-reported (if a subject is unable to provide self-report, other reporters include parent/care giver or health care provider).

- **Injection Site Erythema**

Injection site erythema is a redness of the skin caused by dilatation and congestion of the capillaries localized at the injection site. It can best be described by looking and measuring.

- **Injection Site Swelling/Induration**

Injection site swelling is a visible enlargement of an injected limb. It may be either soft (typically) or firm (less typical). Injection site induration is a palpable thickening, firmness, or hardening of soft tissue, usually has well-demarcated palpable borders, can be visible (raised or sunken compared to surrounding skin), is often ‘woody’ to touch and has a flat shape. As differentiation between swelling and induration may be difficult without health care professional’s assessment, both symptoms have been combined to allow self-assessment by the subjects. Both swelling and induration can best be described by looking and measuring.

*Note:* Any other injection site events not meeting the above case definitions should be reported separately as unsolicited AEs.

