### 12.1.3. Severity Criteria

All AEs and laboratory data reported as AEs will be coded for severity using the toxicity grading table in [Attachment 1](#) (for Cohort 0), and in [Attachment 2](#) (for Cohort 1). *Note:* For Cohort 0, laboratory values within local laboratory normal ranges (even if within a toxicity grade range), or laboratory values outside normal ranges that are not clinically significant in the judgment of the investigator, should not be recorded as AEs. For AEs not identified in the grading table, the following guidelines will be applied:

**Mild (Grade 1):** Awareness of symptoms that are easily tolerated, causing minimal discomfort and not interfering with everyday activities.

**Moderate (Grade 2):** Sufficient discomfort is present to cause interference with normal activity.

**Severe (Grade 3):** Extreme distress, causing significant impairment of functioning or incapacitation. Prevents normal everyday activities.

**Potentially life-threatening (Grade 4):** Symptoms causing inability to perform basic self-care functions OR medical or operative intervention indicated to prevent permanent impairment, persistent disability.

The investigator should use clinical judgment in assessing the severity of events not directly experienced by the subject (eg, laboratory abnormalities).

For Cohort 0, the toxicity grading scale used for laboratory assessments is based on the FDA toxicity grading table, consistent with the assessment grading used throughout the protocol. If a laboratory value falls within the grading as specified in the FDA table, but also within the laboratory normal limits, the value is considered as normal. For hemoglobin, both the actual value and the change from reference will be graded.

The severity of solicited AEs will be graded in the diary by the subject based on the severity assessment provided in the diary and then verified by the investigator using the respective toxicity grading table.

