**A: Tables for Clinical Abnormalities**

Local Reaction to Injectable Product	Mild (Grade 1)	Moderate (Grade 2)	Severe (Grade 3)	Potentially Life-threatening (Grade 4)
Pain	Does not interfere with activity	Repeated use of non-narcotic pain reliever > 24 hours or interferes with activity	Any use of narcotic pain reliever or prevents daily activity	Emergency room visit or hospitalization
Tenderness	Mild discomfort to Touch	Discomfort with Movement	Significant discomfort at rest	Emergency room visit or Hospitalization
Erythema/redness*	2.5 – 5 cm	5.1 – 10 cm	> 10 cm	Necrosis or exfoliative dermatitis
Induration/swelling**	2.5 – 5 cm and does not interfere with activity	5.1 – 10 cm or interferes with activity	> 10 cm or prevents daily activity	Necrosis

\* In addition to grading the measured local reaction at the greatest single diameter, the measurement should be recorded as a continuous variable.

\*\* Induration/Swelling should be evaluated and graded using the functional scale as well as the actual measurement.

Vital Signs *	Mild (Grade 1)	Moderate (Grade 2)	Severe (Grade 3)	Potentially Life-threatening (Grade 4)
Fever** (°C)	38.0 – 38.4	38.5 – 38.9	39.0 – 40	>40
Fever** (°F)	100.4 – 101.1	101.2 – 102.0	102.1 – 104	>104
Tachycardia - beats per minute	101 – 115	116 – 130	>130	Emergency room visit or hospitalization for arrhythmia
Bradycardia - beats per minute***	50 – 54	45 – 49	< 45	Emergency room visit or hospitalization for arrhythmia
Hypertension (systolic) - mm Hg	141 – 150	151 – 155	>155	Emergency room visit or hospitalization for malignant hypertension
Hypertension (diastolic) - mm Hg	91 – 95	96 – 100	>100	Emergency room visit or hospitalization for malignant hypertension
Hypotension (systolic) - mm Hg	85 – 89	80 – 84	< 80	Emergency room visit or hospitalization for hypotensive shock
Respiratory Rate - breaths per minute	17 – 20	21 – 25	>25	Intubation

\* Subject should be at rest for all vital sign measurements.

\*\* Oral temperature; no recent hot or cold beverages or smoking.

\*\*\* When resting heart rate is between 60 - 100 beats per minute. Use clinical judgment when characterizing bradycardia among some healthy subject populations, for example, conditioned athletes.

Systemic (General)	Mild (Grade 1)	Moderate (Grade 2)	Severe (Grade 3)	Potentially Life-threatening (Grade 4)

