Pain/tenderness at injection site	Mild discomfort when the injection site is touched; child does not limit use of his/her arm or leg where the injection was done.	Notable discomfort when the injection site is touched; child limits use of his/her arm or leg where the injection was done.	Severe discomfort when the injection site is touched; child avoids use of his/her arm or leg where the injection was done.	Emergency room visit or hospitalization and significant medical intervention/therapy required.
Erythema/redness	≥10 and <25 mm diameter.	≥25 and <50 mm diameter.	≥50mm diameter.	Emergency room visit or hospitalization; necrosis or exfoliative dermatitis.
Induration/swelling	≥10 and <25 mm diameter.	≥25 and <50 mm diameter.	≥50mm diameter.	Emergency room visit or hospitalization; necrosis or exfoliative dermatitis.
Itching at the injection site	Infrequent, brief episode of scratching, easily distracted from scratching.	Frequent, longer episodes of scratching, difficult to distract.	Near constant scratching, or scratching during sleep; excoriation of skin.	Itching over entire body. Emergency room visit or hospitalization.
Edema	≥10 and <25 mm diameter.	≥25 and <50 mm diameter.	≥50mm diameter.	Emergency room visit or hospitalization; necrosis or exfoliative dermatitis.
Rash at the injection site	≥10 and <25 mm diameter.	≥25 and <50 mm diameter.	≥50mm diameter.	Emergency room visit or hospitalization; necrosis or exfoliative dermatitis.

Reactogenicity	Grade 1	Grade 2	Grade 3	Grade 4
Systemic reactions				
Allergic reaction	Pruritus without rash.	Pruritic rash.	Mild urticaria.	Severe urticaria anaphylaxis, angioedema. Emergency room visit or hospitalization and significant medical intervention/therapy required.
Irritable/Fussy/Crying/Screaming	Easily consoled and returns to play easily. He/she has periods of crying fewer than 60 minutes.	Not easily consoled and is not easily interested in playing. He/she has periods of crying lasting between 60-120 minutes.	Very irritable, cannot be consoled and does not play. He/she has periods of continuous crying lasting more than 2 hours.	Inconsolable. Emergency room visit or hospitalization and significant medical intervention/therapy required.

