### 5.1. Adverse Events (AE)

#### 5.1.1. Definitions

Solicited AEs shown in the tables are extracted from the diary pages of the CRF. For unsolicited AEs, only the AEs starting (grade and/or relation) within the 28-day period following each vaccination will be presented in the safety tables except for SAE, which will be captured and tabulated in the outputs covering the whole study period. All other collected unsolicited adverse events will be presented through listings.

Solicited local AEs will be by definition considered as related to the study vaccine.

The severity of the AEs will be classified as grade 1 to 4. Solicited events that are graded less than grade 1, are not considered as AE. In case no grades are available, the grading of the solicited events will occur according to the grading list in [Attachment 1](#).

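### Swelling is to be graded on a functional scale in all subjects, but the toddler table has no such scale and the SAP does not say which grade is analysed

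*Protocol*

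**What the plan says.** The instruction to grade by function appears twice. The synopsis (Safety Evaluations) lists, among the solicited local events for all subjects, "swelling/induration (measured using the ruler supplied and graded using the functional scale), and pain/tenderness". Section 9.2.3 (Injection Site (Local) Adverse Events) adds: "Induration/swelling should also be graded using the functional scale". That section treats the parent or guardian as the subject for pediatric participants, and neither place restricts the instruction to adults.

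The grading tables differ by cohort. Protocol Attachment 1, for Cohort 0, combines size and function. Its Grade 1 for swelling is "2.5 – 5 cm and does not interfere with activity", and its footnote says "Induration/Swelling should be evaluated and graded using the functional scale as well as the actual measurement". Protocol Attachment 2, for Cohort 1, starts at "Induration/swelling ≥10 and <25 mm diameter", continues with "≥25 and <50 mm diameter" for Grade 2, and sets Grade 3 at 50 mm or more. Its Grade 4 is defined by emergency visit, hospitalization, necrosis or exfoliative dermatitis. SAP Attachment 2 has the same rows.

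Section 12.1.3 assigns Attachment 1 to Cohort 0 and Attachment 2 to Cohort 1. Solicited events are graded in the diary and "then verified by the investigator using the respective toxicity grading table".

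SAP 5.1.1 takes solicited AEs from the diary pages of the CRF and states: "Solicited events that are graded less than grade 1, are not considered as AE". Where no grade is available, it sends the event to SAP Attachment 1.

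**The concern.** Parents are asked for a grade for which their cohort's table has no scale, and the investigator then checks it against a table with no functional criterion for swelling. If the toddler diary carries a functional item, a diary grade and a diameter grade can disagree, and nothing says how to combine them or which to tabulate.

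Solicited local AEs are a primary endpoint. SAP 5.1.2 tabulates them by any occurrence, worst grade and Grade 3. Because SAP 5.1.1 drops anything below Grade 1, the choice of scale can affect whether a small swelling counts at all, as well as how severe it is called.

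**Working it through.** The documents give no figure to reproduce, so the check sets the texts side by side.

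**Step 1. Is there a functional scale for toddler swelling?** Protocol Attachment 1 has one, for adults. Protocol Attachment 2 and SAP Attachment 2 have none. Limb use appears in the toddler table only in the pain/tenderness row. A functional swelling grade for a toddler therefore cannot be derived from the documents.

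**Step 2. Does a later rule settle the grade?**
- Section 12.1.3 has the investigator verify the diary grade, but does not say that the verified grade replaces the one on the CRF diary pages that SAP 5.1.1 uses.
- SAP Attachment 3 keeps on-site and Day 1 diary assessments as separate records when they differ. It has no rule for function against diameter.
- For events lasting beyond Day 8, SAP Attachment 3 has the CRF hold maximum severity, diameter, or both for local AEs, so the two can exist as separate items.
- No section in the body of the SAP cites its Attachment 2 as a grading table. The one citation, in 5.1.3, concerns diary conversion, which is in Attachment 3.

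**Step 3. Does the missing-grade rule work for toddlers?** In the copy reviewed, SAP Attachment 1 holds laboratory, urine and vital-sign rows and no local reactions. Adding the adult rows from Protocol Attachment 1 would not help. Adult Grade 1 starts at 2.5 cm = 25 mm and adult Grade 3 by size is above 10 cm = 100 mm, against 10 mm and 50 mm in Attachment 2. A 15 mm swelling that does not interfere with activity is Grade 1 for a toddler and ungraded in the adult table.

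**Step 4. How could grades differ?** This illustration assumes that the adult functional wording is borrowed for toddlers, which the documents do not say.

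| Swelling | Activity | Attachment 2 | Adult functional wording |
|---|---|---|---|
| 8 mm | interfered with | below Grade 1, no AE | Grade 2 |
| 20 mm | interfered with | Grade 1 | Grade 2 |
| 60 mm | not interfered with | Grade 3 | Grade 1 |

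The first row changes the any-AE count. The second changes only the worst-grade table. The third changes the Grade 3 count if the functional grade replaces the diameter grade, but not if the worse of the two is taken.

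**Step 5. Size per toddler.** Protocol Tables 1 and 5 give 24 active and 12 placebo toddlers. In the by-regimen tables, one toddler crossing a reported threshold moves the rate by 1/24 = 4.2 points or 1/12 = 8.3 points. SAP Table 1 still lists 32 and 16, which would give 1/32 = 3.1 and 1/16 = 6.3 points. The Protocol numbers are used here because they match the 36 toddlers in SAP 1.2.

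**The case against.** The best defence is that Cohort 1 has only one swelling scale. Section 12.1.3 says that severity is coded by Attachment 2 and has the investigator check the diary against it. SAP Attachment 2 reproduces that table cut down to the solicited events, which points to it as the intended analysis scale. The diary is not among the documents, so whether parents see a functional item is unknown. Safety is analysed descriptively, with no formal testing. The pausing rule for solicited events covers systemic events only, and the functional wording in the adult table stops at Grade 3, so the Grade 4 trigger is untouched. Amendment 4 reports 35 toddlers enrolled by 18 April 2019, so changing collection wording now does little.

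Much of this stands. A reader might infer that the same toddler reaction does receive two different grades. The documents show only that it can. A reader might also infer that refusal to use a leg makes a small swelling Grade 3, or that pain is counted twice as swelling. Both import the pain row's limb-use criterion into swelling, which no table does.

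The defence does not remove the conflict. A toddler diary with a functional scale departs from Attachment 2, and one without departs from the synopsis and 9.2.3. The SAP neither names the governing grade nor sends missing Cohort 1 grades to the right table.

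**Conclusion.** The inconsistency is real. A functional grade is required for toddler swelling, no toddler scale for it exists, and the SAP does not say which grade enters the tables. Its fallback for missing grades points away from the Cohort 1 table. The absence of local-reaction rows in SAP Attachment 1 is judged from the copy reviewed; the wrong-cohort reference does not depend on it.

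The effect is confined to descriptive counts in a primary endpoint: severity, and AE status for swellings under 10 mm. The 4.2 and 8.3 points apply only when a toddler crosses the threshold being reported; a move from Grade 1 to Grade 2 changes neither the any-AE nor the Grade 3 rate. It is tempting to turn this into an expected number of misgraded toddlers. The documents give neither a swelling rate nor a rate of disagreement between scales, so any such total would rest on invented inputs. No hypothesis test, sample size or solicited-event pausing rule is affected.

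**What to change.** In the Protocol synopsis and Section 9.2.3, limit functional grading of induration/swelling to Cohort 0, so that both agree with Section 12.1.3 and Attachment 2.

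In SAP 5.1.1, state for Cohort 1 that:
- Grades 1 to 3 of induration/swelling are derived from the recorded largest diameter by Attachment 2;
- Grade 4 stays outcome-based, as in Attachment 2;
- missing grades are assigned by Attachment 2, not Attachment 1;
- any functional grade already collected is listed and not tabulated.

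The cost is wording in two Protocol places and a few sentences in one SAP section. The largest diameter is already recorded daily, so the rule also covers toddlers already enrolled without new data. Where only a severity was captured after Day 8, the SAP should say that it is listed as collected. Defining a toddler functional scale with a combining rule would also be coherent, but with 35 toddlers enrolled it could not be applied to most diaries. The SAP text is the part that matters most now.

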## STATISTICAL METHODS

### Sample Size Determination

The number of subjects chosen for this study will provide a preliminary safety and immunogenicity assessment. Placebo recipients are included for blinding and safety purposes and will provide additional control specimens for immunogenicity assays.

While mild to moderate vaccine reactions (local site and systemic responses) are expected, AEs that preclude further dose administration or more serious ones that would limit product development are not anticipated.

The following table shows the probabilities of observing at least one AE at given true AE rates:

True AE rate	Probability of observing at least one AE in N subjects			
	N=4	N=8	N=12	N=24
0.5%	2%	4%	6%	11%
1%	4%	8%	11%	21%
2.5%	10%	18%	26%	46%
5%	19%	34%	46%	71%
10%	34%	57%	72%	92%
25%	68%	90%	97%	100%
50%	94%	100%	100%	100%

a Recommended orally for adult subjects; rectally or axillary for pediatric subjects (actual routes to be recorded in the eCRF).

